2.5. Treatments

The BTM is designed to be implanted into a newly debrided wound bed and stapled or sutured to the edge of the wound. The BTM provides a scaffold to facilitate dermal repair whilst keeping the wound physiologically ‘closed to reduce wound contraction’. When integration is complete, typically within 28 to 35 days, the combined bonding layer and sealing membrane is peeled off, or can be left in place longer (>30 days) if more time is required for donor skin graft preparation, and discarded leaving only the implanted foam layer to biodegrade.

The BTM device is not intended to be used on the hands, face, neck, plantar skin, or perineal area.

3. General Statistical Considerations

Continuous variables will be summarized using the appropriate descriptive statistics: number of observations (n), mean, standard deviation (SD), median, minimum, and maximum. Categorical variables will be summarized using the frequency and percentage of observed data. All tabulated data will be presented in subject level listings as source data. In general, no formal inferential statistics are to be performed due to the small sample size unless specified otherwise in the statistical analysis plan.

For the summary statistics of all numerical variables unless otherwise specified, minimum and maximum will be displayed to the same level of precision as reported. Mean and median will be displayed to one level of precision greater than the data collected. The standard deviation or standard error will be displayed to two levels of precision greater than the data collected.

Due to the small sample sizes, all p-values derived from inferential analyses will be considered informative. In general, all significant testing will be two-sided at significance level 0.05. All tests will be made without adjustment for multiplicity or multiple comparisons. P-values will be rounded to four decimal places. If a p-value is less than 0.0001 it will be reported as "<0.0001". If a p-value is greater than 0.9999 it will be reported as ">0.9999".

When frequencies are presented, the percentage will be suppressed when the count is zero in order to draw attention to the non-zero counts. A row denoted "Missing" will be included in count tabulations where necessary to account for dropouts or missing data. The denominator for all percentages will be the number of subjects within the analysis population of interest, unless otherwise specified.

Unless otherwise specified, Baseline will be defined as the last non-missing assessment prior to the start of an investigated procedure. Subjects will be identified in the listings by a unique subject number.

All analyses will be conducted using SAS Version 9.2 or higher

3.1. Sample Size

Sample size (N=10) was determined to be adequate to obtain initial data, while minimizing risk to the subjects. No formal statistical sample size calculations have been made.

3.2. Randomization, Stratification, and Blinding

No randomization or stratification will be implemented as this is an open-label study.

3.3. Analysis Populations

Two study populations are defined in this study including Screening, and Intent-to-Treat (ITT).

3.3.1. Screening Population

The Screening Population is defined as the set of subjects who provided informed consent and have at least one screening assessment.

3.3.2. ITT Population

The Intent-to-Treat (ITT) Population consists of all subjects treated with a BTM. All safety and efficacy analyses will be performed using the ITT population.

3.4 DSMB Meetings

Formal meetings of the DSMB will be conducted after 2 subjects complete the 7 to 10 days post SSG time point (calculated from the time of BTM application until 7 to 10 days after SSG application). The DSMB will meet again and all subjects will be reviewed after the 10th subject passes the 7 to 10 days post SSG time point 7-10 day and after the 10th subject passes the 3 month post SSG follow-up visit.

4. Subject Disposition

4.1. Disposition

The number and percentage of subjects in the Screening and ITT Populations will be summarized by sites for screening population.

The number and percentage of subjects who discontinue the study early will be presented for the ITT population. Reasons for early discontinuation will be summarized in categories recorded in the eCRFs.

A listing of subject disposition and population data will be also presented for the Screening population.

4.2. Protocol Deviations

A protocol deviation is any noncompliance with the clinical trial protocol, Good Clinical Practices, Manual of Operations, or other applicable requirements. Noncompliance may be due to the subject, Investigator, or trial staff. Protocol deviations will be categorized into major and non-major deviations. Major deviations are departures from the protocol that impact subject safety or data integrity.

The protocol deviations/violations will be identified and assessed by the clinical monitor of the sponsor or designee following company standard operational procedure.

A summary table by types of protocol deviation and a by-subject listing with protocol deviations will be provided based on the ITT population.

5. Demographics and Baseline Characteristics

5.1. Demographics

Demographic data consists of age in years (Equation 1), age group which will be categorized as: young adults (18 to 35 years), middle-aged adults (36 to 55 years), and older adults (≥ 55 years), sex, race, and ethnicity. The subject level Baseline characteristics consist of Baseline height in cm, Baseline weight in kg, body mass index (BMI) in kg/m², Fitzpatrick Skin Type Scale, Burn Etiology, and %TBSA Affected by Deep Dermal/Full-Thickness. A summary of demographics and subject level Baseline characteristics will be presented for the ITT population using either descriptive statistics or frequency and percentages. Age will be calculated as:

Equation 1:

Age = greatest integer $\leq [(informed\ consent\ date - date\ of\ birth + 1) / 365.25]$.

Wound level Baseline characteristics such as depth and size in %TBSA will be summarized by frequency and percentages and descriptive statistics respectively for the ITT population.

All other Baseline characteristics for safety and efficacy assessments will be summarized in efficacy and safety reports respectively if applicable.

5.2. Medical History

A summary of medical and surgical history will be presented by body system as recorded in the eCRF. A by-subject listing will be also provided.

5.3. Inclusion and Exclusion Criteria

Subjects who meet all of the protocol defined inclusion criteria and none of the exclusion criteria will be enrolled into the study. Inclusion/exclusion criteria data will be presented in a listing for the Screening Population.

6. Treatments and Medications

6.1. Prior and Concomitant Medications/Non-Drug Therapies/Burn Therapies

All medications taken within 30 days prior to the date of study screening will be recorded in the eCRF. Concomitant medication will be coded according to the World Health Organization Drug Dictionary (WHODD, version 01SEP2015). A prior medication is defined as any medication that has a stop date before the date of implantation of BTM. A concomitant medication is defined as any medication that has a stop date during the treatment-emergent period or beyond.

The number and percentage of subjects who used prior or concomitant medications will be summarized by preferred term for the ITT population. A listing for prior or concomitant medications will also be provided.

Imputation for missing medication stop dates can be found in Appendix 12.3.

Medications with missing stop dates after imputation will be classified as both prior and concomitant.

Furthermore, Non-Drug Therapies and Burn Therapies will be presented in a listing.

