12.3. Missing AE onset dates imputation

For the purpose of inclusion in AE tables, incomplete AE onset dates will be imputed as follows:

Missing day only:

- If the month and year are the same as the BTM implantation month and year, then the date of the BTM implantation will be assigned to the missing day.
- If the month and year are before the month and year of the BTM implantation, then the last day of the month will be assigned to the missing day.
- If the month and year are after the month and year of the BTM implantation, then the first day of the month will be assigned to the missing day.

Missing day and month or missing month only:

- If the year is the same as the BTM implantation, and the end date (after any imputation) is prior to the BTM implantation, then the date of the BTM implantation will be assigned to the missing fields.
- If the year is before the year of BTM implantation, then December 31 will be assigned to the missing fields.
- If the year is after the year of BTM implantation, then January 1 will be assigned to the missing fields.

If year is missing, onset date will not be imputed. If the end date is non-missing and the imputed onset date is after the end date, the onset date will be imputed by the end date.

For the purpose of inclusion in prior and concomitant medication tables, incomplete medication stop dates will be imputed as follows:

- If only the day is missing, then 15th will be assigned to the missing day.
- If only the month is missing, then June will be assigned to the missing month.
- If both day and month are missing, then June 15th will be assigned to the missing month and day.
- If year is missing, stop date will not be imputed.

If the imputed medication stop date is before the medication start date, the stop date will be imputed by the end date.

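### SAP 6.1 also counts as prior some drugs first given after BTM implantation, and the stop-date fallback in SAP 12.3 cannot be executed

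*SAP*

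**What the plan says.** SAP 6.1 gives two definitions, both based on the stop date: "A prior medication is defined as any medication that has a stop date before the date of implantation of BTM", and "A concomitant medication is defined as any medication that has a stop date during the treatment-emergent period or beyond". Neither uses the start date. It then deals with whatever remains unresolved: "Medications with missing stop dates after imputation will be classified as both prior and concomitant". The resulting classes feed a table of subject counts and percentages by preferred term in the ITT population, plus a listing.

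The medication imputation rules are at the end of SAP Appendix 12.3:

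- Day missing: "If only the day is missing, then 15th will be assigned to the missing day".
- Day and month missing: "If both day and month are missing, then June 15th will be assigned to the missing month and day".
- Year missing: "If year is missing, stop date will not be imputed".
- Imputed stop before start: "If the imputed medication stop date is before the medication start date, the stop date will be imputed by the end date".

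Neither section has a rule for drugs that are still being taken.

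**The concern.** A drug still in use has no stop date, and SAP 12.3 does not create one when the year is absent. The catch-all in SAP 6.1 then places it in both classes, even if it was started months after implantation. This can readily occur: concomitant medications are reviewed at every visit and telephone call to 12 months after grafting (protocol 6.7 and Appendix 1), and protocol 7.2 leaves usual and investigator-chosen medication unrestricted.

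The fallback is a different kind of fault. For a medication, the stop date and the end date are the same item. A programmer who reaches that branch has to invent a rule, which defeats the purpose of writing one in advance. What is at stake is whether the prior-medication table means what its title says, and whether the medication tables can be reproduced from the SAP.

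**Working it through.** The plan gives no figure to reproduce. The check applies the rules literally to test records. Assumptions: an illustrative implantation date of 20 June 2018, and a treatment-emergent period that starts at implantation (the SAP does not define it).

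**Conflict with the definition.** If start ≥ implantation and stop ≥ start, then stop ≥ implantation. A drug started on or after implantation can therefore never have a stop date before it, and can never be prior under the SAP 6.1 definition. The catch-all nevertheless calls it prior whenever the stop date is missing.

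| Record | Start | Stop | Result under the SAP |
|---|---|---|---|
| A | 25 June | none (ongoing) | both prior and concomitant |
| B | 1 June | none (ongoing) | both |
| C | 22 June | day unknown, June 2018 | imputed 15 June, before start: fallback |
| D | 1 July | 2018 only | imputed 15 June, before start: fallback |
| E | 1 June | 5 July | concomitant only |
| F | 25 June | 5 July | concomitant only |

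A and F start on the same day, after implantation. They differ only in whether a stop date was recorded, yet A is also counted as prior. For B, started before implantation, the catch-all is a reasonable treatment.

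**The fallback.** In C and D the stop date is to be replaced by an end date, which is the same incomplete field. If the program then treats the date as still missing, the catch-all makes both records prior as well, although both drugs started after implantation. The adverse-event paragraph just above uses similar wording, "the onset date will be imputed by the end date", but there onset and end are two separate fields and the rule requires the end date to be present. It works for events and fails for medications.

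**When the branch is reached.** These counts are illustrative and assume uniform dates.

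- Stop day missing, start and stop in the same 30-day month: any start after the 15th reaches it, which is 15 of 30 start days. Of the 30 × 31 / 2 = 465 possible start/stop pairs, 15 × 16 / 2 = 120 have such a start: 120 / 465 = 25.8%.
- Only the stop year known, start in that same year: any start after 15 June reaches it. That date is day 31 + 28 + 31 + 30 + 31 + 15 = 166, so 365 − 166 = 199 of 365 start days (54.5%).

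These are shares of records that already have the stated part missing. The documents do not say how common such records are.

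**The case against.** The strongest reply is that the SAP never says an ongoing drug has a missing stop date. The eCRF may carry an ongoing status, and a drug known to be continuing can be read as running into the treatment-emergent period or beyond, hence concomitant only. The eCRF is not in the documents, so this stands as a qualification. No SAP rule uses such a status, however, and a drug started after implantation whose stop year is simply unknown meets the catch-all either way.

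It can also be said that the catch-all is a deliberate tie-break for indeterminate records. That is fair for starts before implantation. It does not cover later starts, where the start date alone rules out prior use. If the fallback meant end of study or some other date, the SAP does not say so; the rule is then undefined rather than circular, and still cannot be programmed.

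A reader might infer three further faults that the documents do not support.

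- **That the 15th and June conventions are wrong because, unlike the adverse-event rule, they ignore implantation.** Medication stop and event onset are different fields, and the obvious alternative is not clearly better. Take implantation and stop days uniform on a 30 × 30 grid within one month, before any start-date check. The 15th rule errs in 120 + 105 = 225 of 900 cells (25.0%). Calling a drug prior only when the known part of the date proves it errs in 30 × 29 / 2 = 435 of 900 (48.3%). The choice is one of error direction.
- **That drugs drop out of the concomitant table under the catch-all.** They do not; they appear in both.
- **That infection or take results are affected.** SAP 7.1 and 8.2 do not use medication class.

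**Conclusion.** Both rules are wrong as written, with minor severity. Followed literally, SAP 6.1 adds drugs first given after implantation to the prior-medication table, against its own definition, whenever their stop date is still missing. For ongoing drugs this holds unless the eCRF and programming treat ongoing status separately. The SAP 12.3 fallback has no executable meaning under any definition given.

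The number of records affected cannot be estimated from the documents. The effect is confined to descriptive counts by preferred term in a study of about 10 to 15 subjects, and the medication listing lets a reader see the individual records. No primary or secondary endpoint, adverse-event count or inference depends on the classification.

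**What to change.** In SAP 6.1, add that a medication whose start date is on or after implantation is concomitant only. Limit the catch-all to medications that started before implantation, or whose start is unknown, and whose stop date is missing or ongoing.

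In SAP 12.3, replace the end date in the medication fallback with a defined date that is no earlier than the start date and agrees with the known part of the stop date, such as the last day of the known stop month or year. Setting the stop to the start date is less suitable. With a start of 18 June, implantation on 20 June and a stop day unknown in June, it would make the drug prior although nothing shows that it ended before implantation. The last day of the month makes it concomitant.

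Under these changes records A, C and D become concomitant only, and B, E and F are unchanged. The 15th and June conventions can stay. The cost is a few sentences in the SAP and a small programming change, with no new data collection.

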6.2. Study Treatments

The sole investigational device in this traditional feasibility trial is the BTM. It is supplied with the seal factory-fenestrated and in pieces 20 cm x 40 cm. These can either be cut to size (for smaller wounds) or joined side-to-side (not overlapped) by stapling at seams (in large wounds). No special preparation of the BTM is necessary.

6.2.1. Extent of Exposure (Time to delaminate)

There is no Extent of Exposure analysis applicable for this study.

6.2.2. Treatment Compliance and Modifications

There is no Treatment Compliance analysis applicable for this study.

7. Efficacy Analysis

All efficacy analyses will be conducted using the ITT population. Wound and subject level listings will be presented primarily for all efficacy endpoints. The summary tables will be provided by body regions captured in the eCRFs if applicable. Tables for value change or shift from baseline by visits or other time points will also be given for efficacy points with both baseline and multiple post baseline values.

7.1. Primary Efficacy Endpoint

The primary efficacy endpoints include the BTM 'take' rate and SSG 'take' rate.

7.1.1. BTM 'take' rate

Amount of BTM that is viable (taken) at the time of skin grafting, expressed as a percentage of the total amount of BTM applied.

$$\%BTM \text{ 'Take' rate} = \left(\frac{\%TBSA \text{ covered by BTM that has adhered at time of SSG}}{\%TBSA \text{ treated with BTM}} \right) \times 100$$

Wound level BTM 'take' rate will be captured in the eCRFs and the subject level one will be calculated by dividing the total 'take' %TBSA by total BTM treated %TBSA for each given subject. Both subject and wound level BTM 'take' rate will be present in a listing.

Evidence of BTM integration, i.e. adherence, color, loss of foam pattern, and vascularization, if available, will be listed by BTM-treated lesions.

Descriptive table of BTM 'take' rate at both subject and wound level by age group and gender will be reported as appropriate.

7.1.2. SSG 'take' rate

Applied skin graft which remains viable ('taken') expressed as a percentage of the total amount of BTM-treated SSG applied 7 -10 days after application of the SSG.

$$\%SSG \text{ 'Take' rate} = \left(\frac{\%TBSA \text{ of viable SSG applied over BTM}}{\%TBSA \text{ of treated SSG applied over BTM}} \right) \times 100$$

Same analysis approach as BTM 'take' rate will be conducted for SSG 'take' rate.

7.2. Secondary/Exploratory Efficacy Endpoint

7.2.1. Clinical assessment of wound closure at BTM-treated wound site

Assessments of wound closure such as wound closure percentage, wound closure status, dressing requirement or any other aspects of clinical interest will be presented primarily at each visit using wound level listing. A descriptive table will be provided for wound closure percentage by visit. Another table will report count and percentages of wound closure status (yes or no) by visits. The count and percentages for the wounds which were assessed as 'closed' (yes) at least once will be presented in the same table as well.

7.2.2. Operator ease-of-use as determined by the physician survey

Listing of physician survey scores will be provided with individual score and total score for the four questions.

7.2.3. Joint Contracture Severity and Degree of Motion

Assessments on joint contracture such as joint contracture severity, degree of motion, range of motion test and the cause of the contracture will be presented primarily at each visit using joint level listing. Shift table from baseline to the worst post baseline and from baseline to '7-10 days post SSG time point' in terms of joint contracture severity will also be given at joint level.

7.2.4. Modified Vancouver Scar Scale

Assessments of Modified Vancouver Scar Scale (mVSS) such as pigmentation, vascularity, pliability, height and the corresponding individual and total scores will be presented primarily at each visit using wound level listing. Summary table will be provided for individual and total score respectively by body region and visit using descriptive statistics. Additional descriptive summary table will be provided for individual and total score respectively by visit regardless of body region and subject.

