### 11.3 Effectiveness Review

BTM /integration 'take' rate is measured at time of skin grafting and is defined in the formula below:

Effectiveness for %BTM 'take' rate and %SSG 'take' rate will be calculated 7 - 10 days after application of SSG and are defined in the formulas below:

%BTM 'Take' rate =

$$\left( \frac{\% \text{TBSA covered by BTM that has adhered at time of SSG}}{\% \text{TBSA treated with BTM}} \right) \times 100$$

%SSG 'Take' rate =

$$\left( \frac{\% \text{TBSA of viable SSG applied over BTM}}{\% \text{TBSA treated SSG}} \right) \times 100$$

Baseline range of motion (ROM) of joints (evaluated immediately after eschar removal) will be compared with follow-up measurements and will be summarized using n, mean, SD, median, minimum, and maximum by joint and presented in a listing.

Joint Contracture Severity Scale will be summarized using n and percent to summarize by severity category and presented in a listing.

Wound Closure will be summarized using n and percent and presented in a listing.

Modified Vancouver Scar Scale (mVSS) evaluated at 2, 3, 6 and 12 months after SSG will be summarized using number of observations (n) in each category by visit and presented in a listing.

Severity of pruritus as assessed by the Numerical Response Scale (NRS) at SSG 'take' (7 - 10 days after application of SSG) and 1, 2, 3, 6, and 12 months post SSG will be summarized using n, mean, SD, median, minimum, and maximum by visit and presented in a listing.

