2.4.2. Secondary/Exploratory Endpoints

- Incidence and severity of infections in BTM-treated areas, and the success of treatment of local infections with BTM in place.
- Clinical assessment of % wound closure.
- Operator ease of use as determined by the physician survey (Appendix 12.2).

- Joint contracture at 1, 2, 3, 6, and 12 months after treatment compared with baseline. This will be assessed by Joint Contracture Severity Scale and Range of Motion (ROM) of joints (Appendix 12.2).
- Scar appearance/quality in BTM -treated subjects as assessed by Modified Vancouver Scar Scale (mVSS) (Appendix 12.2) at 2, 3, 6, and 12 months after SSG.
- Pruritus incidence and severity as assessed by NRS at SSG ‘take’ and 1, 2, 3, 6, and 12 months after SSG (Appendix 12.2).

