7.2.5. Pruritus assessed by numerical rating scale and disability

Assessments of pruritus such as duration (hours per day), Numerical Rating Scale (NRS) score and disability will be presented primarily at each visit using wound level listings. A table will be provided for summary statistics of NRS score by visit at wound level. Additional descriptive summary table will be provided for NRS score by visit regardless of body region and subject. Another table will report count and percentages of disability by visits at wound level as well.

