AE = adverse event; ~ = approximately; BTM = biodegradable temporizing matrix; β -hCG = human chorionic gonadotropin; m = months; Numerical Rating Scale (NRS), mVSS modified Vancouver Scar Scale; ROM = range of motion; SSG = split-skin graft; wk = weeks

The visit windows are intended as a guide to the investigators standard of care.

^a Note that in cases of multiple BTM implantations subjects will continued to be reviewed every 3-5 days until final SSG

^b Note that post SSG follow-up visits will occur once the final SSG has been applied

^c Follow-up performed via telephone (not in-person visits).

^d Assessment of infection includes clinical diagnosis supported by confirmatory laboratory findings.

12.2.SCALES

All detailed procedures for each scale will be included in the **Site Manual of Operations**.

Pruritus:

Numerical Rating Scale (NRS):

0	1	2	3	4	5	6	7	8	9	10
No							Worst			
Itch							Imaginable			
							Itch			

Range of Motion (ROM):

ROM measurement (measured with goniometer for each affected joint)

Joint Contracture Severity Scale

- 1=mild
- 2=moderate
- 3=severe

Modified Vancouver Scar Scale (mVSS):

Measured for each lesion

Pigmentation:

- 0 – Normal color (resembles nearby skin)
- 1 – Hypopigmentation
- 2 – Hyperpigmentation
- 3 – Combination/Mixed

Vascularity:

- 0 – Normal
- 1 – Pink (slightly increased in local blood supply)
- 2 – Red (significant increase in the local blood supply)
- 3 – Purple (excessive local blood supply)

Pliability

- 0 – Normal
- 1 – Supple (flexible with minimal resistance)
- 2 – Yielding (giving way to pressure)
- 3 – Firm (solid/inflexible, not easily moved, resistant to manual pressure)
- 4 – Banding (rope-like, blanches with extension of scar, does not limit range of motion)
- 5 – Contracture (permanent shortening of scar producing deformity or distortion, limits range of motion)

Height (mm) of burn lesion

- 0 – Normal (flat)
- 1 - <2
- 2 - >2 and <5
- 3 - ≥5

Total Score: _____

Surgeon's Assessment of BTM Application:

BTM is easy to use:

- 1 – Strongly Agree
- 2 – Agree
- 3 – Neutral
- 4 – Disagree
- 5 – Strongly Disagree

BTM is easy to apply:

- 1 – Strongly Agree
- 2 – Agree
- 3 – Neutral
- 4 – Disagree

5 – Strongly Disagree

BTM is easy to delaminate:

- 1 – Strongly Agree
- 2 – Agree
- 3 – Neutral
- 4 – Disagree
- 5 – Strongly Disagree

BTM is a product I would use for burn patients:

- 1 – Strongly Agree
- 2 – Agree
- 3 – Neutral
- 4 – Disagree
- 5 – Strongly Disagree

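### SAP 7.2.4 drops the category counts that Protocol 11.3 specifies for the mVSS items, and SAP 7.2.5 plans no count for the pruritus incidence endpoint

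*SAP*

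**What the plan says.** **Scar scale.** Protocol 11.3 states that mVSS at 2, 3, 6 and 12 months after grafting "will be summarized using number of observations (n) in each category by visit" and be listed. SAP 7.2.4 makes the wound-level listing the main presentation and adds two tables. For the first: "Summary table will be provided for individual and total score respectively by body region and visit using descriptive statistics". For the second: "Additional descriptive summary table will be provided for individual and total score respectively by visit regardless of body region and subject". Neither sentence mentions counts or categories.

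**Meaning of the term.** SAP Section 3 gives the statistics: "Continuous variables will be summarized using the appropriate descriptive statistics: number of observations (n), mean, standard deviation (SD), median, minimum, and maximum". Its next sentence assigns frequency and percentage to categorical variables. SAP 5.1 treats the two forms as alternatives, to be chosen by type of variable.

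**The pigmentation item.** In SAP 12.2, as in Protocol Appendix 2, code 0 is normal color, 1 hypopigmentation, 2 hyperpigmentation and 3 "Combination/Mixed".

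**Pruritus.** Protocol 2.2 and SAP 2.4.2 name both incidence and severity of pruritus, assessed by NRS, as an endpoint, and SAP 2.2 names both as an objective. SAP 7.2.5 plans three tables. The first is described so: "A table will be provided for summary statistics of NRS score by visit at wound level". The second also covers the NRS score but is pooled across regions and subjects, and the third gives disability for each wound. Protocol 11.3 likewise summarizes severity only.

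**The concern.** The protocol specifies one form of mVSS summary and the SAP plans another, with no stated reason. A programmer who follows 7.2.4 will produce means and SDs of the item scores and will not produce the protocol's table. For vascularity, pliability and height, whose codes run from better to worse, that loses detail. For pigmentation the resulting figures cannot be interpreted, because a higher code is a different kind of color change and not a worse one.

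For pruritus, half of a named endpoint has no planned summary in either document.

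The trial exists largely to judge whether its endpoints suit a pivotal trial. A scar table that cannot show which color change occurred, and an itch table that cannot show how many subjects itch, serve that purpose poorly.

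**Working it through.** The documents give no figure to reproduce on this point. The check is a comparison of texts, followed by an illustration with assumed counts.

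**1. Does any SAP sentence supply the mVSS counts?**
- 7.2.4 calls for descriptive statistics of individual and total scores. It does not use the word mean.
- Section 3 ties descriptive statistics to n, mean, SD, median, minimum and maximum, for continuous variables.
- 5.1 sets descriptive statistics against frequency and percentages.
- Where the SAP wants counts it says so, as for closure status (7.2.1) and disability (7.2.5).

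The natural reading is that the items receive the six continuous statistics. The categorical rule in Section 3 leaves a doubt but does not override the specific text.

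**2. Can the six statistics stand in for the counts?** Assume ten wounds, with counts for pigmentation codes 0, 1, 2, 3.

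| | Set A | Set B |
|---|---|---|
| Counts | 1, 3, 3, 3 | 2, 0, 6, 2 |
| n | 10 | 10 |
| Sum of codes | 0+3+6+9 = 18 | 0+0+12+6 = 18 |
| Mean | 18/10 = 1.8 | 18/10 = 1.8 |
| Sum of squares | 0+3+12+27 = 42 | 0+0+24+18 = 42 |
| SD | √((42 − 10×1.8²)/9) = √(9.6/9) = 1.03 | same |
| Fifth and sixth ordered values | 2, 2 | 2, 2 |
| Median | 2 | 2 |
| Minimum, maximum | 0, 3 | 0, 3 |
| Hypopigmentation | 3/10 = 30% | 0/10 = 0% |
| Hyperpigmentation | 3/10 = 30% | 6/10 = 60% |

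All six statistics agree and the scar patterns do not. The pair is not unique. Any two sets whose counts differ by (1, −3, 3, −1) share n (1−3+3−1 = 0), sum (0−3+6−3 = 0) and sum of squares (0−3+12−9 = 0), and so share mean and SD. The median and range need a separate check, done here for this pair.

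The mean alone misleads more easily. Five wounds coded 1 and five coded 3 give (5×1 + 5×3)/10 = 2.0. That is the code for hyperpigmentation, although no wound has hyperpigmentation alone.

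**3. The total score.** The item maxima are 3 + 3 + 5 + 3 = 14, so pigmentation can supply up to 3/14 = 21% of the total. The printed scale defines that total, and descriptive statistics for it follow the instrument.

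**4. Can itch incidence be read from the NRS tables?** SAP 12.2 labels 0 as no itch. A minimum of 0 shows only that at least one assessed wound was free of itch, and a minimum above 0 shows that none was. Otherwise the six statistics do not fix the number of wounds with itch. Because the tables are over wounds, they cannot give the number of subjects with itch.

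**The case against.** The strongest reply on mVSS has four parts. Section 3 lists the six statistics for continuous variables and gives categorical variables frequencies, so pigmentation could fall under the second rule. Protocol 11.4 leaves full details to the SAP. The wound-level listing is the main presentation and, with 10 to 15 subjects, the counts can be rebuilt from it. Sets A and B were chosen to match, which shows that identical tables are possible, not that they are likely.

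Much of this stands. The SAP wording is ambiguous rather than an explicit replacement of counts, and no information is lost from the trial record. But detail left to the SAP does not explain the omission of a table that the protocol specifies, and a reader should not have to rebuild that table by hand. The pigmentation mean is uninterpretable whether or not two tables happen to coincide.

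Two stronger readings are tempting and are not supported:

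- **That the lack of a subject-level mVSS or NRS table is an error.** SAP 2.4.2 does say "Scar appearance/quality in BTM -treated subjects as assessed by Modified Vancouver Scar Scale (mVSS", where Protocol 2.2 says wounds, and pooled wound tables let a subject with many wounds weigh more. But Protocol 7.1 has these scales assessed per wound region or site, both scale appendices have mVSS measured for each lesion, and Protocol 11.3 requires no subject-level summary. The word subjects may simply name the population.
- **That wound-level percentages would be divided by subjects.** Section 3 makes subjects the default base unless otherwise specified. But 5.1, 7.2.1 and the disability table in 7.2.5 name wounds as the unit, and the rule of percentages of observed data largely settles which wounds count.

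**Conclusion.** Two points hold. SAP 7.2.4 does not carry over the by-category mVSS counts of Protocol 11.3, and its stated method gives pigmentation statistics that cannot be interpreted. SAP 7.2.5 leaves the incidence part of the pruritus endpoint without a summary.

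The consequence is limited to secondary descriptive tables. The take rates and adverse event summaries are untouched, and no test is distorted because the study has no hypothesis. The text comparison rests on no assumption. The 30% against 0% contrast rests on assumed wound counts, since the documents give none, and shows what the planned table could hide rather than what it will hide.

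A subject-level summary of mVSS and NRS beside the pooled tables would be a useful option. Its absence is not a fault in the plan.

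**What to change.** - **SAP 7.2.4:** tabulate each mVSS item (pigmentation, vascularity, pliability, height) by category count and visit, as in Protocol 11.3. Keep descriptive statistics for the total score, if wished with a footnote that up to 3 of its 14 points are pigmentation codes.
- **SAP 7.2.5:** add, by visit, the number and percentage of subjects with any itch, and of treated wounds assessed with any itch. Define any itch, for example as NRS above 0, and for a subject as above 0 in any treated wound.
- **Optional:** a by-visit subject-level summary of mVSS total and NRS beside the pooled wound tables.

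The cost is a few SAP sentences and one or two tables from data already collected. No visit or assessment changes.
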